5.2 RANDOMIZATION

The study will be randomized 1:1 UT-15C to placebo. All subjects will be randomly allocated to receive UT-15C or placebo through the IVRS/IWRS using a centrally administered stratified permuted block randomization by type of background therapy (Strata 1: PDE5-I and sGC stimulator; Strata 2: ERA) which will be balanced across the two treatment groups. Subjects will also be stratified by Baseline 6MWD (less than or equal to 350 meters and greater than 350 meters). Block sizes will be variable and not disclosed to Investigators so that no inferences can be made about possible treatment assignments of current or future subjects.

Prior to randomization, site personnel should complete a Pre-Baseline Review Form for review and approval by the Medical Monitor.

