10.2 SAMPLE SIZE

Approximately 205 adjudicated events will provide at least 90% power with a Type I error rate of 0.05 (two-sided hypothesis) to detect a difference in the time to clinical worsening between treatment groups, assuming exponential distributions and an underlying hazard ratio of 0.62. Assuming a placebo median event time of 32 months (which corresponds to an event rate of 23% at Month 12), this hazard ratio corresponds to a median time to event of 51 months for the UT-15C group, or an event rate of 15% at Month 12. If accrual of subjects is completed during the first three years and 10% of the subjects drop out by the end of the study, a total sample size of at least 610 subjects with a maximum of 850 subjects is expected to generate approximately 205 adjudicated events over the course of the study.

Based on the results of other PAH studies, (e.g., AMBITION [ambrisentan and tadalafil] and GRIPHON [selexipag]; Galiè, 2015; Sitbon, 2015) an interim analysis for efficacy is planned when 75% of the total adjudicated worsening events have occurred. In order to control the total alpha at a two-sided 0.05 level, the method of Lan and DeMets with O'Brien-Fleming-type alpha spending function will be used to calculate the boundaries for stopping the study for efficacy at the interim analysis [Lan and DeMets, 1983]. If the interim analysis is performed with 154 events, the boundary on the p-value scale will be 0.020 and 0.044 for the final analysis. Calculations will be performed in EAST version 6.4, Cytel Inc, using simulated power.

If enrollment continues beyond the interim efficacy analysis, final enrollment will be stopped when approximately 190 clinical worsening (morbidity or mortality) events have been reported by Investigators and reviewed by the Medical Monitor. Subjects will be followed until the occurrence of approximately 205 adjudicated clinical worsening events, at which time all remaining subjects will be transitioned to the open-label extension study. No more than 850 subjects will be enrolled.

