#### 4.2 INTERIM EFFICACY ANALYSIS

One interim analysis for efficacy is planned when 75% (154 events) of the total (205) adjudicated clinical worsening events have occurred. All analyses will be prepared by an independent external consultant and reviewed only by the independent DMC as defined in the DMC charter. The sponsor will only have access to blinded study data during this process. The details of the interim efficacy analysis will be included in a separate SAP for interim analyses.

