##### 10.1.1.1 *Hypothesis*

The study is designed to determine the efficacy of UT-15C compared with placebo in subjects with PAH. The null hypothesis tested for the primary endpoint of time to adjudicated clinical worsening is that there is no difference in hazard ratio in the time to clinical worsening of PAH when treated with UT-15C compared with placebo:

$$H_0: \text{hazard ratio} = 1$$

The 2-sided alternative hypothesis is that there is a difference:

$$H_a: \text{hazard ratio} \neq 1$$

Due to the alpha spending on interim analysis, for the final analysis, the significance level for the primary efficacy analysis of time to adjudicated clinical worsening is 0.044.

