### ***10.1.1.3 Sensitivity and Subgroup Analyses***

The primary efficacy analysis of time to adjudicated clinical worsening events will also be provided for the Per-protocol Population.

The following sensitivity analyses will be performed:

- For all subjects who drop out from the study early, they are considered as having a clinical worsening event. Time to event will be calculated from randomization to subject's discontinuation date.
- For all subjects who drop out from the study early due to AEs, they are considered as having a clinical worsening event. Time to event is calculated from randomization to subject's study discontinuation date.

The time from randomization to clinical worsening will also be compared between treatment groups using a Cox proportional-hazards regression model, adjusting for Baseline 6MWD category ( $\leq 350$  meters versus  $> 350$  meters) and background PAH therapy (as a categorical variable: PDE5-I/sGC stimulator or ERA). Hazard ratio and its 95% confidence interval will be calculated. SAS Procedure PHREG will be used and the pseudo SAS statements are listed below:

```
proc phreg;
  Model TimeToWorsening*Censor_Status(1) = treatment;
  Strata BGTX B_6MWD / risklimits ties=efron;
run;
```

where BGTX variable denotes the background therapy and B\_6MWD denotes the Baseline 6MWD category  $\leq 350$  meters versus  $> 350$ .

Subgroup analyses will be performed on the following factors: background PAH therapy, PAH etiology, Baseline WHO FC, age group (<65 years versus  $\geq 65$  years), Baseline 6MWD category, sex (male versus female), maximum dose achieved (<9 mg versus  $\geq 9$ mg total daily dose), and geographic region as specified in Section 8.2. The estimated hazard ratio between the active and placebo groups from this model will be calculated and displayed along with its 95% confidence interval on the summary and analysis table and plot.

Since clinical worsening is a composite endpoint, the following components of this composite endpoint will also be summarized and analyzed with the same approach as the composite endpoint:

- Time to death (all causes) during the study
- Time to hospitalization due to worsening PAH

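### The only hazard ratio planned for the primary endpoint carries an ordinary 95% interval that does not match the 0.020/0.044 test levels: a small reporting mismatch with a cheap fix

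*SAP*

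**What the plan says.** The primary analysis is a log-rank test stratified by background therapy and Baseline 6MWD category (SAP 10.1.1.2). It is tested twice. SAP 4.2 states: "One interim analysis for efficacy is planned when 75% (154 events) of the total (205) adjudicated clinical worsening events have occurred". Protocol 10.2 and SAP 5 and 8.4 give the two-sided levels as 0.020 at the interim and 0.044 at the final analysis, from an O'Brien-Fleming-type spending function. SAP 10.1.1.1 confirms that at the final analysis "the significance level for the primary efficacy analysis of time to adjudicated clinical worsening is 0.044".

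SAP 10.1.1.2 produces Kaplan-Meier summaries and a p-value, but no hazard ratio. The hazard ratio comes from a stratified Cox model in SAP 10.1.1.3, under the sensitivity and subgroup heading, with the instruction "Hazard ratio and its 95% confidence interval will be calculated". The accompanying code asks for risk limits without setting a confidence level. Neither document mentions a 95.6%, repeated or stage-wise interval or a bias-adjusted estimate, and neither says that the 95% interval is descriptive only. SAP 4.2 adds: "The details of the interim efficacy analysis will be included in a separate SAP for interim analyses". That plan is not among the documents reviewed.

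**The concern.** The hazard ratio and its interval will be read as the size of the treatment effect, because no other effect measure comparing the arms is planned for this endpoint. Readers treat a 95% interval that excludes 1 as a positive result. Here the final test is stricter than that, so a failed primary test could be printed next to an interval that appears to show success. The mismatch runs in one direction only: the interval can exclude 1 when the test does not reject, never the reverse.

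Estimation after an early stop is a separate matter. If the trial stops because the interim result crossed the boundary, the ordinary Cox estimate has been selected for being extreme. That comes from the stopping rule and not from the confidence level, so changing the level alone does not correct the point estimate.

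**Working it through.** **Inputs.** 205 events in total and an interim at 154 (Protocol 10.2, SAP 4.2); levels 0.020 and 0.044; design assumption "assuming exponential distributions and an underlying hazard ratio of 0.62"; "The study will be randomized 1:1 UT-15C to placebo" (Protocol 5.2). Working assumption: SE(log HR) = 2/√events, which is the 1:1 normal approximation without stratification.

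**1. The plan's own figures.**
- Power = Φ(|ln 0.62| × √205/2 − z) = Φ(3.422 − z). With z = 1.960 this is 92.8%; with z = 2.014 (level 0.044) it is 92.0%. The two-look calculation gives 92.4%. The stated power of at least 90% is reproduced.
- Lan-DeMets O'Brien-Fleming spending at 154/205 = 0.751 gives nominal levels 0.0194 and 0.0442. The stated 0.044 is reproduced, and 0.020 is 0.0194 rounded up. Used as written, the two levels give an overall two-sided error of 0.0501.

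**2. Where test and interval part.** The largest hazard ratio that is significant for benefit is exp(−z × 2/√events).
- Final test (z = 2.014): exp(−2.014 × 0.1397) = 0.755.
- Final 95% interval excludes 1 (z = 1.960): exp(−1.960 × 0.1397) = 0.760.
- Interim test (z = 2.326): exp(−2.326 × 0.1612) = 0.687.
- Interim 95% interval excludes 1: 0.729.

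At the final analysis the disagreement zone is about 0.755 to 0.760. At an interim efficacy stop the hazard ratio is at most 0.687, so a 95% interval always excludes 1 and cannot contradict the decision.

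**3. Example.** A final hazard ratio of 0.7575 has p = 0.047 and fails the test. The ordinary 95% interval is 0.576 to 0.996, the 95.6% interval 0.572 to 1.004, and the stage-wise 95% interval 0.578 to 1.003. The last two agree with the test.

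**4. How often.** 4 million simulated trials per true hazard ratio, with correlation √(154/205) between looks:

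| True HR | Test rejects | Plain 95% CI excludes 1 | Disagreement | Coverage of plain 95% CI |
|---|---|---|---|---|
| 1.00 | 5.02% | 5.55% | 0.5% | 94.5% |
| 0.85 | 21.0% | 22.4% | 1.4% | 94.7% |
| 0.75 | 53.1% | 55.0% | 1.9% | 95.0% |
| 0.70 | 71.5% | 73.2% | 1.6% | 95.0% |
| 0.62 | 92.4% | 93.1% | 0.7% | 95.0% |

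With intervals matched to the boundaries (98% at an interim stop, 95.6% at the final analysis), coverage at HR 1 is 94.98%. The interval then excludes 1 in 5.02% of null trials, the same as the test.

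**5. After an early stop.**

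| True HR | Probability of interim stop | Mean HR given a stop | Mean HR over all trials | Plain 95% coverage given a stop |
|---|---|---|---|---|
| 0.75 | 29% | 0.621 | 0.740 | 91.5% |
| 0.70 | 46% | 0.608 | 0.689 | 94.5% |
| 0.62 | 74% | 0.578 | 0.612 | 96.6% |

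(Means are taken on the log scale.) Stage-wise ordering does not help here. After a stop at the only interim, the outcomes ranked as more extreme are just the larger interim statistics, so the median-unbiased estimate and its interval equal the ordinary ones. For an observed 0.62 the 95% limits are 0.452 to 0.850 either way. A Whitehead-type estimate, which solves for the true value whose expected estimate equals the one observed, moves 0.62 to 0.629 and 0.687 to 0.698.

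**The case against.** The strongest reply is that the log-rank p-value is the primary analysis, its level is stated without ambiguity, and the Cox model is listed among sensitivity analyses. No decision uses its interval, and a conventional 95% interval beside a sequentially adjusted p-value is a recognised reporting choice. The disagreement zone is about 0.006 wide on the hazard ratio scale. All of this stands, and it is why the point concerns reporting only. It does not remove the mismatch: this is still the only hazard ratio planned for the primary endpoint, and the SAP does not call its interval descriptive.

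A reader might go further and infer that Type I error is not controlled, or that the planned hazard ratio would be seriously misleading after an early stop. The documents do not support either reading. The test is judged at the two boundaries, which together give 0.0501, in line with the intended 0.05. On early stopping, conditional coverage falls below nominal when the true effect is weaker than planned (91.5% at 0.75), but at the design value it is 96.6%, and the average bias over all trials is slight. The separate interim SAP may also set out estimation after a stop. Its absence here is no evidence that nothing is planned.

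**Conclusion.** The concern holds as a small inconsistency in reporting. The planned 95% interval matches neither the 0.044 final level nor the 0.020 interim level. A visible contradiction can arise only at the final analysis, for p between 0.044 and 0.05. Its probability is at most about 1.9% over the hazard ratios examined and 0.7% under the design assumption. The validity of the test, the power and the event target are unaffected.

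Selection after an early stop is a real but modest effect: the mean hazard ratio given a stop is 0.578 when the truth is 0.62. Whether it is already handled cannot be settled without the interim SAP.

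These figures rest on the normal approximation, exactly 154 and 205 events, and the boundaries as written. A stratified log-rank test and a Wald interval from the Cox model can also differ slightly for unrelated reasons. The change is best described as a cheap improvement.

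**What to change.** In SAP 10.1.1.3:
- At the final analysis, report the Cox hazard ratio with a 95.6% interval, or a 95% interval based on stage-wise ordering.
- If the trial stops at the interim, report a 98% interval.
- State that the plain 95% interval is descriptive and that inference rests on the log-rank p-value against the boundary in force.
- If the interim SAP does not already cover it, name a bias-adjusted hazard ratio, for example a Whitehead-type estimate, to show beside the Cox estimate after an early stop. Do not rely on the stage-wise median-unbiased estimate, which equals the Cox value at the only interim. The 98% interval also leaves the point estimate unchanged.

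This should be settled before unblinding, because an interval chosen after seeing p = 0.047 would not be credible.

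The cost is a few sentences, a confidence-level option in the code and a short routine for the adjusted estimate. The final interval becomes 2.8% wider on the log scale (2.014/1.960 = 1.028). The interim interval becomes about 19% wider (2.326/1.960 = 1.187); for an observed 0.62 it would be 0.426 to 0.902. Matched intervals are somewhat conservative when the drug works, with overall coverage about 96.8% for true hazard ratios of 0.62 to 0.75.

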3 EXPERIMENTAL PLAN

3.1 STUDY DESIGN

This is an international, multi-center, randomized, double-blind, placebo-controlled, event driven study in subjects with PAH. Subjects will be assessed during the Screening period to determine eligibility for the study, which will be confirmed during the Baseline visit prior to randomization. Once randomized, subjects will return for study visits every 4 weeks for the first 12 weeks, then every 12 weeks for the duration of the study. Subjects will continue in the study until either they experience clinical worsening as defined in the protocol, approximately 205 adjudicated events have occurred, or they prematurely discontinue participation in the study for any reason other than protocol-specific clinical worsening. If a subject meets the definition of clinical worsening during the study and receives only short term (28 days or less) treatment with an infused or inhaled PGI₂ therapy for worsening PAH, they will be permitted to enter the open-label extension study (TDE-PH-311). If a subject prematurely discontinues the study for any reason other than clinical worsening, or receives long-term (29 days or more) treatment with an infused or inhaled PGI₂ therapy for worsening PAH, they will not be permitted to enter the open-label extension study. Otherwise, all subjects actively participating in the study will be allowed to transition to the open-label extension study after approximately 205 adjudicated clinical worsening events have occurred.

At each scheduled visit, subjects will undergo the following efficacy assessments: clinical worsening, exercise capacity (6MWD and Borg dyspnea score), and WHO Functional Class. Plasma samples will also be collected for measurement of NT-proBNP at Baseline, Week 12

Week 24, Continued Visit 1 and at every other Continued Visit thereafter. See [Table 3-1](#) for the overall schedule of times and events.

Additionally, subjects may participate in an optional hemodynamic sub-study in which hemodynamic parameters will be assessed by RHC before randomization and following 24 weeks of treatment with study drug.

Safety will be assessed via vital signs, AEs, and clinical laboratory parameters. Subjects will also undergo a 12-lead ECG at Screening and Week 24. At every protocol-required visit, measures of exercise capacity will occur within 3 to 6 hours following administration of the last dose of study drug.

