### 5 SAMPLE SIZE CONSIDERATIONS

Approximately 205 adjudicated clinical worsening events will provide at least 90% power with a type I error rate of 0.05 (2-sided hypothesis) to detect a difference in the time to clinical worsening between treatment groups, assuming exponential distributions and an underlying hazard ratio of 0.62. Assuming a placebo median event time of 32 months (which corresponds to an event rate of 23% at Month 12), this hazard ratio corresponds to a median time to event of 51 months for the UT-15C group (which corresponds to an event rate of 15% at Month 12). Further assuming subject accrual is completed during the first 3 years with a 10% dropout rate at the end of the study, a total sample size of at least 610 subjects with a maximum of 850 subjects is expected to generate approximately 205 adjudicated clinical worsening events over the course of the study.

The primary efficacy endpoint of time to adjudicated clinical worsening events will be tested at an interim analysis when 75% of total adjudicated clinical worsening events have occurred with an alpha level of 0.020, and at the final analysis at an alpha of 0.044 with the overall Type I error rate at 0.05. Efficacy boundaries for early stopping of the study for efficacy are calculated based on O'Brien-Fleming alpha-spending function.

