#### ***10.1.1.2 Primary Efficacy Analyses***

Data on the Clinical Worsening Assessment page of the eCRF will be used in determining clinical worsening status. Investigator-reported clinical worsening events will be reported directly from the eCRF data, regardless of the outcome of the adjudication committee review. An independent adjudication committee will be utilized to adjudicate all investigator-reported clinical worsening events. Adjudicated clinical worsening events will be reported using data received from the adjudication committee.

Subjects who discontinue study drug for reasons other than clinical worsening will be censored at the time of discontinuation of the study drug. Non-fatal clinical worsening events that occur more than 7 days after permanent study drug discontinuation will not be included in the summary and analysis of clinical worsening events. However, all deaths within the study follow-up period (30 days after the last study drug dose) will be included as clinical worsening events. Time to clinical worsening will be summarized by treatment group using product-limit estimates calculated by the Kaplan-Meier method, and displayed graphically as Kaplan-Meier curves. A tabular summary of this analysis will include the number of subjects at risk (sample size), estimated median duration, and a 95% confidence interval for the median duration for each treatment group.

For the primary efficacy analysis of time to adjudicated clinical worsening, the log-rank test adjusted for the type of background therapy (PDE5-I or sGC stimulator versus ERA) and the Baseline 6MWD ( $\leq 350$  meters versus  $> 350$  meters) will be used to calculate the p-value for treatment differences in the ITT Population.

The SAS Procedure LIFETEST will be used. The pseudo SAS statements are listed below:

```
proc lifetest;
  time TimeToWorsening*Censor_Status(1);
  strata BGTX B_6MWD / group=Treatment test=all;
run;
```

where BGTX variable denotes the background therapy and B\_6MWD denotes the Baseline 6MWD category ( $\leq 350$  meters versus  $> 350$  meters).

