### 16.3 LIST OF FIGURES

Figure Number	Figure Title
14.2.1.1	Kaplan-Meier Plot of Time to Adjudicated Clinical Worsening Events
14.2.1.2	Kaplan-Meier Plot of Time to Investigator Reported Clinical Worsening Events
14.2.1.3	Kaplan-Meier Plot of Time to Death
14.2.1.4	Kaplan-Meier Plot of Time to Death at the Study Closure
14.2.1.5	Kaplan-Meier Plot of Hospitalization Due to PAH
14.2.1.6	Forest Plot on Subgroup Analyses of Time to Adjudicated Clinical Worsening Events
14.2.2.1	Plot of 6MWD at Week 24 By UT-15C Drug Dose
14.2.2.2	Forest Plot on Subgroup Analyses of 6MWD (meter) at Week 24
14.2.3	Plot of the Combined 6MWD and Borg Dyspnea Score Ranks at Week 24

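### Only two of the five composite components get their own time-to-event analysis, and the planned Kaplan-Meier curve for PAH hospitalisation overstates its incidence as a first event

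*SAP*

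**What the plan says.** The composite in SAP 10.1.1 has five components: death, PAH hospitalisation, start of an inhaled or infused prostacyclin, disease progression, and unsatisfactory long-term response. SAP 10.1.1.3 states that "the following components of this composite endpoint will also be summarized and analyzed with the same approach as the composite endpoint", and names death during the study and PAH hospitalisation. The output lists in SAP 16.1 and 16.3 match: Tables 14.2.1.8 to 14.2.1.10 and Figures 14.2.1.3 to 14.2.1.5 cover these two only.

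The approach carried over is set out in SAP 10.1.1.2: "Time to clinical worsening will be summarized by treatment group using product-limit estimates calculated by the Kaplan-Meier method", with a stratified log-rank test. SAP 10.1.1.3 adds a stratified Cox model. Figure 14.2.1.5 is titled "Kaplan-Meier Plot of Hospitalization Due to PAH".

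Protocol 3.1 sets the exit rule: "Subjects will continue in the study until either they experience clinical worsening as defined in the protocol". Any one of the five components therefore ends participation. SAP 10.1.1.2 also leaves out non-fatal events more than 7 days after study drug is permanently stopped.

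Neither document mentions competing risks or cumulative incidence. The derivation table in SAP 8.5 defines event and censoring status for the composite only. For death, SAP 8.3.1 and 10.1.1.3 add an analysis to study closure that includes subjects who left early or rolled over to the extension study.

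**The concern.** In a component analysis, a subject whose first event is disease progression, prostacyclin start or unsatisfactory response stops contributing at that event. Kaplan-Meier then treats the subject as still able to have a counted hospitalisation later, at the same rate as those who remain. Under the exit rule no such event will be counted in this study, and after death none can occur. One minus Kaplan-Meier is therefore not the proportion of randomised subjects whose first event was a hospitalisation, yet many readers will take the figure that way.

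The three components without a planned separate analysis include the two that rest on walk distance, functional class and symptoms. If the composite is positive, readers will want to know whether death and hospitalisation or these softer components produced the result. The plan does not commit to showing that.

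**Working it through.** **Inputs.** SAP 5 gives the design model: "assuming exponential distributions and an underlying hazard ratio of 0.62", with a placebo median of 32 months. The documents give no component shares or component hazard ratios, so those below are assumptions, shown over a range.

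**1. Reproducing the plan's figures.** The placebo hazard is λ = ln 2/32 = 0.02166 per month, and the UT-15C hazard is 0.62 × 0.02166 = 0.01343.
- UT-15C median: 32/0.62 = 51.6 months (plan: 51).
- Month-12 event rates: 1 − exp(−12λ) = 22.9% and 14.9% (plan: 23% and 15%).
- Power with 205 events (Schoenfeld): Φ(√(205/4) × |ln 0.62| − 1.960) = Φ(3.422 − 1.960) = 92.8%. At the final alpha of 0.044 it is 92.0%. The stated power of at least 90% holds.

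**2. Hospitalisation as first event.** Let s be the share of first events that are hospitalisations, with every component at hazard ratio 0.62.
- One minus Kaplan-Meier: 1 − exp(−sλt).
- Cumulative incidence as first event: s × (1 − exp(−λt)).

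For s = 0.30 and t = 36 months, λt is 0.7798 on placebo and 0.4835 on UT-15C.
- Kaplan-Meier: 1 − exp(−0.2339) = 20.9% and 1 − exp(−0.1450) = 13.5%, a difference of 7.4 points.
- Cumulative incidence: 0.30 × (1 − 0.4585) = 16.2% and 0.30 × (1 − 0.6166) = 11.5%, a difference of 4.7 points.
- Ratio before rounding: 7.36/4.74 = 1.55, an excess of about 55%.

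| Share | Month | Kaplan-Meier, placebo v UT-15C (difference) | First-event incidence (difference) | Excess in difference |
|---|---|---|---|---|
| 20% | 12 | 5.1 v 3.2 (1.9) | 4.6 v 3.0 (1.6) | 18% |
| 20% | 24 | 9.9 v 6.2 (3.6) | 8.1 v 5.5 (2.6) | 40% |
| 20% | 36 | 14.4 v 9.2 (5.2) | 10.8 v 7.7 (3.2) | 65% |
| 30% | 12 | 7.5 v 4.7 (2.8) | 6.9 v 4.5 (2.4) | 16% |
| 30% | 24 | 14.4 v 9.2 (5.2) | 12.2 v 8.3 (3.9) | 34% |
| 30% | 36 | 20.9 v 13.5 (7.4) | 16.2 v 11.5 (4.7) | 55% |
| 40% | 12 | 9.9 v 6.2 (3.6) | 9.2 v 6.0 (3.2) | 13% |
| 40% | 24 | 18.8 v 12.1 (6.7) | 16.2 v 11.0 (5.2) | 29% |
| 40% | 36 | 26.8 v 17.6 (9.2) | 21.7 v 15.3 (6.3) | 46% |

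**3. Other components unaffected by treatment (hazard ratio 1.0).** With s = 0.30, the UT-15C hazards are k = 0.62 × 0.30 × 0.02166 = 0.00403 for hospitalisation and c = 0.70 × 0.02166 = 0.01516 for the rest. First-event incidence at 36 months is k/(k + c) × (1 − exp(−36(k + c))) = 0.210 × 0.499 = 10.5%. The difference is 16.2 − 10.5, or 5.8 points before rounding, against 7.4 by Kaplan-Meier: an excess of about 27%. The excess disappears only if UT-15C raises the hazard of the other components by a factor of about 1.5 to 1.9 (shares 10-60%, months 24-36).

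**4. Only death competing.** Suppose 10% of first events are deaths and both the hospitalisation and the death hazard are unchanged after a non-fatal exit. Incidence at 36 months is (0.30/0.40) × (1 − exp(−0.40λt)) = 20.1% v 13.2%, a difference of 6.9 points. Kaplan-Meier still gives 7.4, an excess of 6.5% (3-10% for death shares of 5-15%).

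**5. Death.** If 10% of first events are deaths, on-study Kaplan-Meier gives 7.5% mortality at 36 months on placebo. If the death hazard after a non-fatal exit is 1, 2, 3 or 5 times that before it, true all-cause mortality is 7.5%, 9.5%, 11.3% or 14.8%. Kaplan-Meier then equals or understates mortality.

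**The case against.** The strongest objection concerns the estimand. The SAP plans time to hospitalisation, not hospitalisation as first event. Disease progression or prostacyclin start does not prevent a later admission; it only ends observation. On that view only death competes, the excess falls to about 6.5% (step 4), and if risk rises after progression Kaplan-Meier could even understate how many are ever hospitalised. This stands as a limit on the size. It does not rescue the curve: with later admissions not counted, the ever-hospitalised reading depends on an untested assumption about risk after exit, while first-event incidence can be estimated from the adjudicated data.

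Three stronger readings are tempting, and the documents do not support them.
- A reader might infer that the trial will report an absolute benefit inflated by about half. No absolute risk difference is a planned output. The tabular summary in SAP 10.1.1.2 gives numbers at risk and medians, so the excess is something a reader would take off the figure. With three years of accrual in a study of about four years, only subjects enrolled in roughly the first year reach month 36.
- A reader might extend the overstatement to death. Step 5 shows the opposite risk, and the study-closure analysis already follows subjects after exit.
- A reader might infer that a positive composite cannot be traced to its components. Adjudicated events are captured and listed, and Table 14.2.1.1 may break them down. The SAP simply does not commit to it.

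The SAP also never states that a subject is censored at another component's event. That is inferred from the carried-over approach and the exit rule, and the silence should be filled.

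**Conclusion.** The point holds for hospitalisation and for the coverage of components. Two of five components have a planned separate time-to-event analysis. One minus Kaplan-Meier overstates first-event hospitalisation in each arm whenever other components occur.

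For the difference between arms, the 29-65% excess at 2-3 years rests on exponential hazards at the design values, an assumed share of 20-40%, and a common hazard ratio of 0.62. It is 13-18% at 12 months, about 27% at 36 months if the other components are unaffected and the share is 30%, and 3-10% if only death competes and risk is unchanged after exit. Overstated benefit is therefore likely but not certain.

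The primary composite test and its power are untouched. The log-rank and Cox results for hospitalisation remain valid as cause-specific comparisons. This is a cheap improvement to a supportive analysis, not a threat to the trial's main conclusion.

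**What to change.** Amend SAP 10.1.1.3 and the output lists before unblinding:

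1. Report first-event counts by arm for all five adjudicated components, with a stated rule for events on the same day (for example, prostacyclin started during a PAH admission).
2. Replace the Kaplan-Meier curve in Figure 14.2.1.5 with Aalen-Johansen cumulative incidence of each component as first event, the others competing. With the same-day rule, the five curves sum to the composite.
3. Keep the stratified Cox hazard ratios, label them cause-specific, and state that subjects are censored at another component's event. They should be read together with the curves: if treatment delays only the other components, more subjects stay at risk and first-event hospitalisation rises on UT-15C. With a 40% share, hospitalisation at hazard ratio 1.0 and the rest at 0.62, it is 1.8 points higher at 36 months while Kaplan-Meier shows no difference.
4. Make the study-closure death analysis the main mortality estimate, with the on-study analysis as support.

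The cost is some SAP wording, one table and a revised figure, using adjudication data already planned and no new data collection. The downside is a little more analysis and a less favourable hospitalisation curve.
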